11.2 Secondary Efficacy

11.2.1 Type I Error Control, Additional Claims and Labeling

Should the primary effectiveness endpoint be found to be statistically significant, additional secondary endpoints will be evaluated for inclusion in the labeling for the device including p-values and 95% confidence intervals. The secondary endpoints are listed in priority order in **Section 11.2.2** Priority Order and Hypothesis Tests and will be evaluated in that order. If statistical significance is achieved for the highest priority endpoint the testing will

move to the next highest until either statistical significance is not reached, or the list has ended. This ordered hypothesis approach permits each hypothesis to be evaluated at two sided $\alpha=0.05$ or equivalently one-sided $\alpha=0.025$ and controls the study-wide Type I error at 5%.

Secondary endpoints or additional analysis outside of those that do support additional claims are supportive in nature and not intended to support additional claims. Data may be included in labelling per agreement with the FDA and will be limited to summary statistics (e.g. mean, standard deviation, minimum, median, maximum, number and percent) and will not include 95% confidence intervals or p-values. For more information about the secondary endpoint analyses see **Section 11.2.3 Secondary Objectives**.

11.2.2 Priority Order and Hypothesis Tests

These hypothesis tests will be evaluated in the FAS population.

- 1. To prove that the mean improvement in QoL scale Bother from baseline to 4-weeks is statistically significantly greater in the treatment group as compared to the sham group.**

Hypothesis:

H_0 : The mean improvement in QoL scale Bother from baseline to 4-weeks in subjects randomized to treatment (μ_T) will be lower than or equal to that in subjects randomized to sham (μ_S), $\mu_T \leq \mu_S$.

H_a : The mean improvement in QoL scale Bother from baseline to 4-weeks in subjects randomized to treatment (μ_T) will be greater than that in subjects randomized to sham (μ_S), $\mu_T > \mu_S$.

Success is defined as a statistically significant difference (at the 0.05 two-sided significance level) between least squared means for randomized groups.

- 2. To prove that the mean improvement in QoL scale Impact from baseline to 4-weeks is statistically significantly greater in the treatment group as compared to the sham group.**

Hypothesis:

H_0 : The mean improvement in QoL scale Impact from baseline to 4-weeks in subjects randomized to treatment (μ_T) will be lower than or equal to that in subjects randomized to sham (μ_S), $\mu_T \leq \mu_S$

H_a : The mean improvement in QoL scale Impact from baseline to 4-weeks in subjects randomized to treatment (μ_T) will be greater than that in subjects randomized to sham (μ_S), $\mu_T > \mu_S$

Success is defined as a statistically significant difference (at the 0.05 two-sided significance level) between least squared means for randomized groups.

3. **To prove that the proportion of patients with improvement of at least 2 grades from baseline to 4-weeks in HDSS is statistically significantly greater in the treatment group as compared to the sham group.**

Hypothesis:

H_0 : The proportion of subjects with improvement of at least 2 grades from baseline to 4 weeks in HDSS in subjects randomized to treatment (p_T) will be lower than or equal to that in subjects randomized to sham (p_S), $p_T \leq p_S$

H_a : The proportion of subjects with improvement of at least 2 grades from baseline to 4 weeks in HDSS in subjects randomized to treatment (p_T) will be greater than that in subjects randomized to sham (p_S), $p_T > p_S$

Success is defined as a statistically significant difference (at the 0.05 two-sided significance level) between proportions of patients with at least 2 grade improvement in HDSS from baseline to 4 weeks between randomized group using CMH test stratified by baseline HDSS (3 vs. 4).

4. **Proportion of subjects with at least 50% improvement in gravimetric sweat production (GSP) in subjects treated with the N-SWEAT Patch only at 4-weeks. (GSP will be calculated based on the total sweat produced by both axillae.)**

H_0 : The proportion of subjects with at least 50% improvement in gravimetric sweat production (GSP) in subjects randomized to treatment (p_T) is not statistically significantly different from 0, $p_T = 0$.

H_a : The proportion of subjects with at least 50% improvement in gravimetric sweat production (GSP) in subjects randomized to treatment (p_T) is statistically significantly different from 0, $p_T \neq 0$.

Success is defined as a statistically significant result (at the 0.05 two-sided significance level). It is expected that at least 50% of subjects will have at least 50% improvement in gravimetric sweat production from baseline at 4-weeks.

11.2.3 Secondary Objectives

11.2.3.1 To compare the mean improvement over baseline for QOL scale Bother between subjects randomized to treatment as compared to sham

Subjects Included in Analysis: All FAS subjects will be included in the analysis.

Endpoint(s): QOL scale Bother score

Statistical Analysis: An analysis will be performed using all available time points with complete follow-up at the time of the analysis. A generalized linear mixed model will be used to compare average change in QOL Bother from baseline to follow-up between randomized groups over time on study. The dependent variable change in QOL Bother from baseline to follow-up with independent variables to include randomized group, follow-up time, baseline HDSS and two-way interaction terms. The covariance structure among the compound symmetric, auto-regressive and unstructured that provides the best model fit by the Schwarz BIC criterion will be chosen.

A hierarchical stepwise backward elimination technique will be used to reduce the model. The two-way interactions will be reviewed first, the two-way interaction with the largest p-value provided that p-value is greater than 0.05 will be removed from the model and the model refit and repeated until only two-way interactions with p-values < 0.05 are retained. The main effects for any two-way interaction retained in the model must remain in the model as well as the randomized treatment. That being said, the main effects will be evaluated in the same manner as the two-way interaction terms. This analysis will be repeated in the PP population.

11.2.3.2 To compare the mean improvement over baseline for QOL scale Impact between subjects randomized to treatment as compared to sham

Subjects Included in Analysis: All FAS subjects will be included in the analysis.

Endpoint(s): QOL scale Impact score

Statistical Analysis: An analysis will be performed using all available time points with complete follow-up at the time of the analysis. A generalized linear mixed model will be used to compare average change in QOL Impact from baseline to follow-up between randomized groups over time on study. The dependent variable change in QOL Impact from baseline to follow-up with independent variables to include randomized group, follow-up time, baseline HDSS and two-way interaction terms. The covariance structure among the compound symmetric, auto-regressive and unstructured that provides the best model fit by the Schwarz BIC criterion will be chosen.

A hierarchical stepwise backward elimination technique will be used to reduce the model. The two-way interactions will be reviewed first, the two-way interaction with the largest p-value provided that p-value is greater than 0.05 will be removed from the model and the model refit and repeated until only two-way interactions with p-values < 0.05 are retained. The main effects for any two-way interaction retained in the model must remain in the model as well as the randomized treatment. That being said, the main effects will be evaluated in the same manner. This analysis will be completed in the PP population as well.

11.2.3.3 To compare the proportion of patients with at least a 2 grade improvement in HDSS from baseline between subjects randomized to treatment as compared to sham

Subjects Included in Analysis: All FAS subjects will be included in the analysis.

Endpoint(s): HDSS.

Statistical Analysis: The proportion of patients with at least a 2 grade improvement in HDSS from baseline to 4 weeks will be compared between treatment vs. sham using the Cochran-Mantel-Haenszel (CMH) test stratified by baseline HDSS value of 3 vs. 4 in the FAS population. Statistical significance is achieved with two-sided p-value <0.05 equivalent to one-sided p-value < 0.025. This analysis will be completed in the PP group as well.

An analysis will be performed using all available time points with complete follow-up at the time of the analysis. A generalized linear mixed model will be used to compare the proportion of subjects with at least 2 grade improvement from baseline to 4 weeks between randomized groups over time on study. The dependent variable is 2 grade improvement over baseline (Y/N) with independent variables to include randomized group, follow-up time, baseline HDSS and two-way interaction terms. The covariance structure among the compound symmetric, auto-regressive and unstructured that provides the best model fit by the Schwarz BIC criterion will be chosen.

A hierarchical stepwise backward elimination technique will be used to reduce the model. The two-way interactions will be reviewed first, the two-way interaction with the largest p-value provided that p-value is greater than 0.05 will be removed from the model and the model refit and repeated until only two-way interactions with p-values < 0.05 are retained. The main effects for any two-way interaction retained in the model must remain in the model as well as the randomized treatment. That being said, the main effects will be evaluated in the same manner as the two-way interactions. This analysis will be completed in the PP group as well.

11.2.3.4 To estimate the proportion of subjects randomized to treatment with at least 50% improvement from baseline to 4 weeks in gravimetric sweat production (GSP)

Subjects Included in Analysis: All FAS subjects randomized to receive the N-SWEAT patch.

Endpoint(s): The average of 2 accurate GSP measurements will be conducted for each Axilla at each time point. The total sweat production at each timepoint will be calculated by summing the average sweat production from both axilla. The percentage change at 4 weeks will be calculated based on the total sweat production at baseline and 4 weeks.

Statistical Analysis: The potential confounding factors of room temperature, room humidity , position during evaluation and time of evaluation will be summarized for baseline and 4 weeks. The difference in temperature, humidity, time of evaluation and whether or not the baseline and 4 week evaluation were performed in the same or different position will be summarized. These factors will be evaluated with respect to their relationship with the endpoint and association with outlying values, if any, using graphical techniques and summary statistics. Depending on this evaluation, outlying values may be excluded from the analysis with justification provided and relationships, if any found, will be summarized.

The proportion of patients with 50% or greater improvement from baseline to 4 weeks will be statistically compared to zero by calculating the Wilson's 95% two-sided confidence interval and comparing the lower bound to zero. If the lower bound is greater than zero, there is statistically

significant evidence that the proportion of subjects with a clinically relevant improvement exists and is greater than 0. This analysis will be completed in the PP population as well.

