6.4 Observational Endpoints

- Baseline-adjusted mean improvement in QoL-7 instrument assessed by treatment group (randomized cohort)
- Composite - proportion of patients with HDSS 1 or 2 AND 50% improvement in GSP assessed by treatment group (randomized cohort)
- Composite - proportion of patients with HDSS 1 or 2 AND 75% improvement in GSP assessed by treatment group (randomized cohort)
- Duration of efficacy: time from treatment to first observed reversion to HDSS 3 or 4 (median duration of efficacy will be calculated) for all N-SWEAT treated subjects. Also performed for first reversion to subject's baseline HDSS.
- Mean change from baseline over time in GSP compared between treatment groups (randomized cohort); Change in GSP at individual timepoints.

CANDESANT BIOMEDICAL	CLINICAL STUDY PROTOCOL SAHARA STUDY	Document #: CB-CLP-001 Revision: E
-------------------------	---	---------------------------------------

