8.3.2 After Confirmation of Eligibility

The Quality of Life (QoL) questionnaires should be completed by the patient to establish the baseline condition. QOL surveys will include: QOL-7, which has a total of 7 questions, QOL (Bother and Impact) which has 2 questions total and an additional survey with up to 5 QoL assessment questions may be included to collect informative data on the patient population. If possible, the subject should complete these surveys electronically.

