8. ASSESSMENT OF COMPARABILITY OF RANDOMIZED GROUPS AND EVALUATION FOR POOLING

8.1 Demographics / Baseline Characteristics and Protocol Administration

Patient disposition will be listed and summarized for the ITT and roll-in data sets by treatment group. Protocol deviations will be collected and summarized by randomized group in the ITT population and roll-in group.

Demographics (age, gender, race/ethnicity) and baseline characteristics (HDSS, GSP, Fitzpatrick skin type, and BMI) will be summarized by treatment group for ITT and roll-in groups.

The randomized groups will be compared at time of randomization for the important demographics and baseline characteristics specified. Should additional important baseline parameters be identified prior to the analysis, they will be evaluated in the same manner. Any of the variables that are significant at a two-sided $\alpha=0.05$ will be evaluated as covariates or strata variables in the primary effectiveness analysis or as an additional or supporting analysis to the primary effectiveness endpoint and if desired, secondary/observational endpoints as well. Continuous variables will be evaluated both as stratification variables by dichotomizing the subjects into two groups based on the median or other appropriate value and as a continuous variable in the statistical models. Logistic regression analysis may be used for the primary efficacy endpoint should it be desirable to evaluate multiple covariates simultaneously in a statistical model.

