11.3 Observational Endpoints

Observational endpoints will be summarized at all available time points at the time of analysis. Observational endpoints are supportive in nature and not intended to support additional claims. Data may be included in labelling per agreement with the FDA and will be limited to summary statistics (e.g. mean, standard deviation, minimum, median, maximum, number and percent) and will not include 95% confidence intervals or p-values. Statistical significance will be determined based on a two-sided p-value of 0.05. The p-values for the observational endpoints will not be adjusted for multiplicity and should be interpreted with caution.

11.3.1 To compare the mean improvement over baseline for QoL-7 between subjects randomized to treatment as compared to sham

Subjects Included in Analysis: All FAS subjects will be included in the analysis.

Endpoint(s): QoL-7 score. The score is calculated by assigning 1 for a yes response and 0 for a no response and summing over the 7 questions.

Statistical Analysis: An analysis will be performed using all available time points with complete follow-up at the time of the analysis. A generalized linear mixed model be used to compare average change in QoL-7 from baseline to follow-up between randomized groups over time on study. The dependent variable change in QoL-7 from baseline to follow-up with independent variables to include randomized group, follow-up time, baseline HDSS and two-way interaction terms. The covariance structure among the compound symmetric, auto-regressive and unstructured that provides the best model fit by the Schwarz BIC criterion will be chosen.

A hierarchical stepwise backward elimination technique will be used to reduce the model. The two-way interactions will be reviewed first, the two-way interaction with the largest p-value provided that p-value is greater than 0.05 will be removed from the model and the model refit and repeated until only two-way interactions with p-values < 0.05 are retained. The main effects for any two-way interaction retained in the model must remain in the model as well as the randomized treatment. That being said, the main effects will be evaluated in the same manner as the two-way interaction terms.

This analysis will be repeated for each of the 7 questions that comprise the QOL-7 and in the PP population.

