Statistical Analysis: A Kaplan-Meier product limit method will be used for the analysis. Time 0 will be the treatment date. For subjects who do not respond to treatment, the duration of treatment will be 0. For subjects who do respond to treatment, the event is the first subsequent week of follow-up after the 4 week follow-up in which the subject reported an HDSS of 3 or 4 or censoring from the study either due to drop-out or completing the study without reverting to HDSS 3 or 4. The study groups will be compared using the Log-Rank statistic stratified by HDSS 3 or 4 at baseline.

This analysis will be completed for reversion to the patient's baseline value and in the PP group as well.

11.3.5 To compare mean change from baseline at 4 weeks in GSP between subjects randomized to treatment as compared to sham.

Subjects Included in Analysis: All FAS subjects will be included in the analysis.

Endpoint(s): The average of 2 accurate GSP measurements will be conducted for each Axilla at each time point. The total sweat production at each timepoint will be calculated by summing the average sweat production from both axilla. The change in GSP at 4 weeks will be calculated by subtracting the total sweat production at baseline from the total value at 4 weeks.

Statistical Analysis: An analysis of variance model will be used to compare average change in total GSP at 4 weeks as compared to baseline between randomized groups. The dependent variable is change in total GSP at 4 weeks as compared to baseline with independent variables to include randomized group, baseline HDSS, and two-way interaction terms.

A hierarchical stepwise backward elimination technique will be used to reduce the model. The two-way interactions will be reviewed first, the two-way interaction with the largest p-value provided that p-value is greater than 0.05 will be removed from the model and the model refit and repeated until only two-way interactions with p-values < 0.05 are retained. The main effects for any two-way interaction retained in the model must remain in the model as well as the randomized treatment. That being said, the main effects will be evaluated in the same manner as the two-way interaction terms. This analysis will be repeated in the PP population.

11.3.6 To compare responses to additional QOL questions from baseline throughout follow-up, as appropriate between subjects randomized to treatment as compared to sham.

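### The models for change in Bother and Impact leave out the outcome's own baseline; adding it costs about one degree of freedom and may gain precision on the first two gatekeeping secondary tests

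*SAP*

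**What the plan says.** For Bother (SAP 11.2.3.1) and Impact (11.2.3.2) the dependent variable is change from baseline in a repeated-measures mixed model, with "independent variables to include randomized group, follow-up time, baseline HDSS and two-way interaction terms". Protocol 9.10.2.3 gives the same covariates. Backward elimination then starts with the interactions and goes on to the main effects: "That being said, the main effects will be evaluated in the same manner as the two-way interaction terms". Only the randomized group and the main effects of retained interactions are protected.

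The observational models follow the same pattern. SAP 11.3.1 reads "The dependent variable change in QoL-7 from baseline to follow-up with independent variables to include randomized group", followed by time, baseline HDSS and interactions. SAP 11.3.5, for GSP change, has "independent variables to include randomized group, baseline HDSS, and two-way interaction terms".

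The baseline scores exist. Protocol 8.3.2, after eligibility is confirmed, states: "The Quality of Life (QoL) questionnaires should be completed by the patient to establish the baseline condition".

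SAP 8.1 provides for extra covariates when a baseline variable differs between groups at two-sided p<0.05. For endpoints other than the primary this applies "if desired, secondary/observational endpoints as well". The variables it names, besides age, gender and race/ethnicity, are in "baseline characteristics (HDSS, GSP, Fitzpatrick skin type, and BMI) will be summarized by treatment group for ITT and roll-in groups". No QoL scale is among them, although further baseline parameters may be identified before the analysis.

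Protocol 6.4 describes one observational endpoint as "Baseline-adjusted mean improvement in QoL-7 instrument assessed by treatment group". It does not define the adjustment, and SAP 11.3.1 drops the term.

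**The concern.** When change from baseline is analysed without the baseline value as a covariate, the slope of follow-up on baseline is in effect fixed at 1. Unless the true slope is close to 1, this leaves avoidable variance in the treatment contrast, and any chance difference in baseline scores passes into the estimate. Baseline HDSS has two levels in this population and is a weak substitute for the score itself; elimination may remove even that.

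Bother and Impact are the first two secondary hypotheses in SAP 11.2.2. If Bother misses, then Impact, the 2-grade HDSS response and the GSP response cannot be claimed. The trial plans about 50 evaluable subjects per arm, a number set by the primary endpoint, and no power is stated for either QoL scale. QoL-7 and GSP change are observational, with no p-values or confidence intervals allowed in labelling, so little is at stake there. The primary CMH test is not involved.

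**Working it through.** **The plan's own figure.** The only sizing is for the primary endpoint (SAP 11.1): 50 per arm for 85% vs 60%, and 45 per arm for 73% vs 44%, at 80% power and two-sided 0.05. The pooled-variance formula is n = [1.96√(2p̄q̄) + 0.8416√(p₁q₁ + p₂q₂)]² / (p₁ − p₂)².
- 85% vs 60%: (1.96√0.39875 + 0.8416√0.3675)² / 0.0625 = 48.9, so 49 per arm (power at 50 is 80.9%).
- 73% vs 44%: (1.96√0.48555 + 0.8416√0.4435)² / 0.0841 = 44.1, so 45 per arm.

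The stated figures reproduce, but they say nothing about power for Bother or Impact.

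**Precision.** SDs and correlations are not in the documents, so these inputs are assumptions. Set the follow-up SD to 1, the baseline SD to k and their correlation to ρ.
- Variance of raw change = 1 + k² − 2ρk
- Variance after own-baseline adjustment = 1 − ρ²
- Ratio R = adjusted / raw
- Effective n per arm = 50 / R
- Power = Φ(2.80/√R − 1.96), starting from an assumed 80%

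Example, k = 1 and ρ = 0.5: R = 0.75/1.00 = 0.75, effective n = 66.7, power = Φ(3.23 − 1.96) = 90%.

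The last column puts HDSS in both models as a linear covariate, with assumed correlation 0.5 with the baseline score and 0.5ρ with follow-up.

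| k | ρ | Raw | Adjusted | R | Effective n | Power | R with HDSS |
|---|---|---|---|---|---|---|---|
| 1.0 | 0.3 | 1.40 | 0.91 | 0.65 | 77 | 94% | 0.71 |
| 1.0 | 0.5 | 1.00 | 0.75 | 0.75 | 67 | 90% | 0.80 |
| 1.0 | 0.7 | 0.60 | 0.51 | 0.85 | 59 | 86% | 0.88 |
| 0.8 | 0.3 | 1.16 | 0.91 | 0.78 | 64 | 88% | 0.83 |
| 0.8 | 0.5 | 0.84 | 0.75 | 0.89 | 56 | 84% | 0.92 |
| 0.8 | 0.7 | 0.52 | 0.51 | 0.98 | 51 | 81% | 0.99 |
| 0.6 | 0.3 | 1.00 | 0.91 | 0.91 | 55 | 83% | 0.93 |
| 0.6 | 0.5 | 0.76 | 0.75 | 0.99 | 51 | 80% | 0.99 |
| 0.6 | 0.7 | 0.52 | 0.51 | 0.98 | 51 | 81% | 0.99 |
| 0.5 | 0.3 | 0.95 | 0.91 | 0.96 | 52 | 82% | 0.97 |
| 0.5 | 0.5 | 0.75 | 0.75 | 1.00 | 50 | 80% | 1.00 |
| 0.5 | 0.7 | 0.55 | 0.51 | 0.93 | 54 | 83% | 0.94 |

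With HDSS in both models, k = 1 gives an effective n of 57 to 70 and power of 85% to 91%; k = 0.6 gives 50.5 to 54 and 80% to 83%.

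**Cost.** Spending one degree of freedom at N = 100 multiplies the variance by about 1 + 1/95. In the worst case (ρ = k, slope exactly 1) the ratio is 1.011 and power is 79.6% instead of 80%.

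**Simulation.** With normal scores, one time point and 40,000 trials per cell, type I error was 0.047 to 0.052 with and without adjustment, and the largest power loss from adjusting was 0.4 points. With a five-level score like the actual items (6,000 runs per setting), power with HDSS only versus with own baseline added was:
- k = 1: 69% vs 83% (ρ = 0.3), 81% vs 89% (0.5), 93% vs 95% (0.7)
- k = 0.6: 78% vs 84%, 86% vs 88%, 94% vs 94%

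Type I error there was 4.5% to 5.5%. HDSS alone gave almost no gain over no covariate.

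**Chance imbalance.** At 50 per arm, p<0.05 in SAP 8.1 needs a baseline gap of 1.96√(2/50) = 0.39 baseline SD. A gap just below this moves the raw-change estimate by |k − ρ| × 0.39 relative to the adjusted one; the standard error of the raw-change difference is √(raw variance × 2/50).
- k = 1, ρ = 0.3 to 0.7: a shift of 0.27 down to 0.12 follow-up SD, or 1.16 down to 0.76 standard errors.
- k = 0.6: a shift of 0.04 to 0.12 SD, or 0.22 to 0.59 standard errors.

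**The case against.** The planned analysis is valid. Randomization protects it, protocol and SAP agree on the Bother and Impact covariates, and study success does not depend on them. This stands: the point concerns efficiency.

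The size is assumed throughout, including the 80% starting power. With a compressed baseline and HDSS already in the model, the gain almost vanishes. This also stands, which is why the range starts at nil. But the loss in the worst case is about 1% of variance, so the uncertainty does not argue against the change.

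The imbalance figures describe a tail. The median chance gap is about 0.6745 × √(2/50) = 0.13 SD, so typical shifts are about a third of those shown. Stratifying on HDSS makes a gap of 0.39 SD rarer still: about 2.4% instead of 5% if HDSS correlates 0.5 with the baseline score, from 2[1 − Φ(1.96/√0.75)]. That is fair, and precision is the main argument.

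SAP 8.1 could admit a QoL baseline through its allowance for further parameters. It could, but it would still act only on a significant difference and remain optional for these endpoints.

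The closed forms and simulations use a single time point, whereas the SAP specifies a repeated-measures model. The percentages are therefore indicative and are not the planned model's exact gain.

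No figure shows harm from dropping HDSS. That is correct; the reason to retain it is that it is the stratification factor and a fixed model removes a data-driven choice.

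**Conclusion.** The concern holds. None of the four change models contains the outcome's own baseline, elimination can remove baseline HDSS, and SAP 8.1 does not reliably fill the gap. Validity is not in question.

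For ρ of 0.3 to 0.7 and k of 0.5 to 1, the variance gain runs from nil to 35%, making 50 per arm act like 50 to 77. Entry limited to HDSS 3 or 4 could narrow the baseline spread, which favours the low end. Because the downside is negligible and the change affects the first two gatekeeping claims, it should be made.

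The missing definition of baseline adjustment for QoL-7 is unresolved wording on one observational endpoint. Protocol 9.10.3 points to methods consistent with the secondary endpoints, so it is not a clear contradiction.

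**What to change.** Amend the SAP before the sponsor is unblinded at the 4-week analysis (SAP 7):

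- Add the outcome's own baseline as a fixed main-effect covariate: Bother in 11.2.3.1, Impact in 11.2.3.2, QoL-7 in 11.3.1 and total GSP in 11.3.5.
- Exempt that term and baseline HDSS from backward elimination in all four models.
- State whether the repeated-measures models include a baseline-by-time term, which is advisable so that the week-4 contrast gets the full gain. State that baseline-by-group and baseline-by-HDSS terms are not included.
- Define in 11.3.1 what baseline adjustment means for QoL-7.

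The cost is a text change, with no new data or subjects and no change to alpha. Each model loses one degree of freedom for the main effect; a baseline-by-time term adds three more if weeks 1 to 4 are modelled as categories.

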An analysis will also be performed using all available time points with complete follow-up at the time of the analysis. A generalized linear mixed model will be used to compare the proportion of subjects with HDSS of 1 or 2 between randomized groups over time on study. The dependent variable is HDSS of 1 or 2 (Y/N) with independent variables to include randomized group, follow-up time, baseline HDSS and two-way interaction terms. The covariance structure among the compound symmetric, auto-regressive and unstructured that provides the best model fit by the Schwarz BIC criterion will be used.

A hierarchical stepwise backward elimination technique will be used to reduce the model. The two-way interactions will be reviewed first, the two-way interaction with the largest p-value provided that p-value is greater than 0.05 will be removed from the model and the model refit and process repeated until only two-way interactions with p-values < 0.05 are retained. The main effects for any two-way interactions retained in the model must remain in the model as well as the randomized treatment. With that said, the main effects will be evaluated in the same manner as two-way interactions. This analysis will be repeated in the PP population as well.

Additional Statistical Analysis Subjects Randomized to Treatment: Logistic regression will be used to evaluate whether there is relationship between the total time that the patch was on both axilla and the primary efficacy endpoint as well as the average and maximum level of pain during treatment and the primary efficacy endpoint. The treatment characteristic will be evaluated as a continuous variable and a categorical variable dichotomized at the median value.

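### For the gatekept 4-week Bother and Impact tests, choosing the covariance by BIC, with no variance estimator or degrees of freedom named, does not guarantee the claimed 5% error

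*SAP*

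**What the plan says.** SAP 11.2.2 places Bother first and Impact second in the ordered secondary tests and sets the criterion for both: "Success is defined as a statistically significant difference (at the 0.05 two-sided significance level) between least squared means for randomized groups". SAP 11.2.1 offers p-values and 95% confidence intervals for labelling along this sequence and says that the ordered approach "controls the study-wide Type I error at 5" percent.

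SAP 11.2.3.1 and 11.2.3.2 define the model for both scores:

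- Data: "An analysis will be performed using all available time points with complete follow-up at the time of the analysis". Protocol 8.8 collects the scores weekly from week 1, so four post-baseline scores exist at week 4.
- Mean model: "independent variables to include randomized group, follow-up time, baseline HDSS and two-way interaction terms".
- Reduction: "A hierarchical stepwise backward elimination technique will be used to reduce the model", at p > 0.05.
- Covariance: "The covariance structure among the compound symmetric, auto-regressive and unstructured that provides the best model fit by the Schwarz BIC criterion will be chosen".

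Protocol 9.10.2.3 has the same covariance rule. Neither document says whether standard errors are model-based or robust, how degrees of freedom are obtained, whether time is categorical, or whether the least squares means are taken at week 4 or averaged over the weeks.

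**The concern.** Compound symmetric and (in its usual form) auto-regressive covariance both assume the same variance at every week. Only unstructured lets week 4 have its own variance, and BIC charges heavily for it at this sample size. If the spread of the change scores differs between weeks and BIC keeps an equal-variance structure, the week-4 contrast is tested with roughly the average variance of weeks 1-4. A model-based standard error is then too small if the SD has risen and too large if it has fallen.

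At stake are two tests that support label statements and that open steps 3 and 4. A standard error that is too small passes the sequence on too often; one that is too large costs power at the first gate. Because the variance estimator is not named, it could also be settled after the data are seen.

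**Working it through.** **Inputs from the documents.** 50 evaluable subjects per arm (SAP 11.1), so n = 100; weekly scores (Protocol 8.8); gatekept tests at 4 weeks (Protocol 6.3, SAP 11.2.2); two-sided 0.05. The claimed 5% cannot be reproduced, because no SD or correlation is given for Bother or Impact. The SDs and correlations below are assumptions, shown as a range.

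**BIC penalty.** With T = 4 visits, unstructured has T(T+1)/2 = 10 parameters; compound symmetric and AR(1) have 2 each. The extra penalty is (10 − 2) × ln(100) = 36.8. A likelihood-ratio statistic of that size on 8 df has p ≈ 0.00001, so equal variance is dropped only on overwhelming evidence.

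**Closed-form check.** Suppose an equal-variance structure is kept and the SD changes linearly over the four weeks. The ratio of the model-based to the true standard error at week 4 is r = √(mean variance) / SD at week 4. The actual error is P(|t| > 1.984 r) on 98 df.

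- SD 0.9 to 1.1: mean variance (0.810 + 0.934 + 1.068 + 1.210)/4 = 1.006; r = 1.003/1.1 = 0.912; error 7.4%.
- SD 0.8 to 1.1: mean variance (0.64 + 0.81 + 1.00 + 1.21)/4 = 0.915; r = 0.957/1.1 = 0.870; error 8.8%. This is an upper figure, because BIC sometimes picks unstructured.
- SD 1.1 to 0.9: r = 1.003/0.9 = 1.114; error 2.9%.

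**Simulation under the null.** 50 per arm, 60/40 split of baseline HDSS 3/4, complete normal data, categorical time, REML fits, BIC with n = 100, model-based t-tests, 20,000 replicates (Monte Carlo SE 0.15 points). Only group-by-time could be eliminated. RI+AR means random intercept plus AR(1).

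| Assumed truth, 4 visits | BIC picks unstructured | Week-4 contrast, BIC choice | Week-4 contrast, unstructured | Final test after elimination |
|---|---|---|---|---|
| Compound symmetric | <0.1% | 4.9% | 5.1% | 5.4% |
| AR(1) | <0.1% | 5.1% | 5.2% | 5.5% |
| RI+AR, constant SD, with or without measurement error | <0.1% | 4.8-5.0% | 5.0-5.1% | 5.9-6.3% |
| RI+AR, SD rising 20% | 0.7% | 7.2% | 5.1% | 6.3% |
| RI+AR, SD rising 30% | 4.3% | 7.9% | 5.1% | 6.4% |
| RI+AR, SD rising 40% | 17.4% | 8.2% | 5.1% | 6.7% |
| RI+AR, SD falling 17% or 23% | 0.5%, 4.3% | 3.0%, 2.5% | 5.1% | 5.6%, 5.5% |

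**Reading the last column.** Under the null, group-by-time drops out in about 95% of trials, leaving a group main effect. With the covariance form correctly chosen, elimination alone gives 5.4-5.5%. Of the 6.3-6.7% in the rising-SD rows, about 0.4-0.5 points can therefore be put down to elimination. A further set of runs (6,000 replicates, SDs of 0.9-1.1, 0.8-1.1 and 0.8-1.2) gave 5.7-6.9% after elimination.

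**Why naming unstructured is not enough.** If the model is still reduced to main effects and naive degrees of freedom are used, the error was about 6.1-6.5% (4,000 replicates). Hence the small-sample correction and the retained group-by-time term in the fix.

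**The case against.** The rule is prespecified, its criterion is objective, and unstructured is on the menu. The error is about 5% when compound symmetry or AR(1) is true, and the week-4 contrast is conservative when the SD falls. Nothing in the documents shows that the SD of Bother or Impact rises, and both are bounded five-category items while the simulations used normal data. The test as written follows backward elimination, so the 7-9% for the full-model contrast overstates what most trials would see. A robust variance with the BIC choice kept gave 5.0-5.5% for the overall group effect at four visits. All of this stands, and it limits the point to a missing guarantee.

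It does not rescue the 5% claim. Equal variance is no better supported than rising variance, BIC will rarely correct a modest departure at this sample size, and the SAP does not name the robust variance that would protect the test.

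Three stronger readings are tempting, and the documents do not support them:

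- A reader might infer that the tests definitely exceed 5%. That depends on a covariance the documents do not give.
- A reader might infer that the SAP prescribes model-based standard errors. It is silent; they are an assumption of the calculation.
- A reader might carry over the 9-13% error found for an overall group effect with 12 visits and a random intercept plus AR(1) truth. That is not the 4-week gatekept test.

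The all-time-point HDSS model in SAP 11.1 ("The covariance structure among the compound symmetric, auto-regressive and unstructured that provides the best model fit by the Schwarz BIC criterion will be used") and the QoL-7 model in SAP 11.3.1 ("A generalized linear mixed model be used to compare average change in QoL-7 from baseline to follow-up between randomized groups over time on study") are supportive. The primary test is the stratified CMH, and the QoL-7 p-values are expressly unadjusted. Neither bears on the 5% claim.

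**Conclusion.** The point holds in limited form: as written, the plan does not guarantee 5% for the Bother and Impact tests. With model-based standard errors, the week-4 contrast has about 7-9% error if the SD rises by roughly 20-40% over weeks 1-4, about 3% if it falls, and about 5% under compound symmetry or AR(1). For the final test after elimination, the rising-SD figure is about 6-7%, and only part of that excess comes from the covariance rule.

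These sizes rest on assumed covariances, complete normal data, categorical time, AR(1) as the auto-regressive form, and elimination of group-by-time only. Which figure applies also turns on whether the least squares means are at week 4 or averaged, which the SAP leaves open. The primary endpoint is unaffected. The change is worth making because it is cheap and removes the dependence on an unknown covariance.

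**What to change.** In SAP 11.2.3.1 and 11.2.3.2, for the 4-week analysis:

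- Replace the BIC choice with unstructured covariance (10 parameters at four visits) and Kenward-Roger degrees of freedom.
- Keep group-by-time in the model, exempt from elimination, and name the week-4 difference in least squares means as the test.
- State one fallback, used only on non-convergence: a named simpler structure with sandwich standard errors.

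In the simulations, the week-4 contrast with prespecified unstructured covariance had 5.0-5.2% error in every four-visit scenario. Sandwich standard errors for the 12-week, binary and QoL-7 models are optional.

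The cost is SAP wording and a slightly wider interval if a simpler structure is true. No change to data collection or sample size is needed.
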